APPENDIX A Performance Scales

MODIFIED LANSKY SCORE (Score as 0 - 100)

- A. Normal Range
 - 100 = Fully active
 - 90 = Minor restrictions in physically strenuous play
 - 80 = Restricted in strenuous play, tires more easily, otherwise active
- B. Mild to moderate restriction
 - 70 = Both greater restrictions of and less time spent in active play
 - 60 = Ambulatory up to 50% of time, limited active play with assistance/supervision
 - 50 = Considerable assistance required for any active play; full able to engage in quiet play
- C. Moderate to severe restriction
 - 40 = Able to initiate quiet activities
 - 30 = Needs considerable assistance for quiet activity
 - 20 = Limited to very passive activity initiated by others e.g. TV)
 - 10 = Completely disabled, not even passive play
 - 0 = Unresponsive, coma

KARNOFSKY SCALE

- 100 = Normal; no complaints
 - 90 = Able to carry on normal activities; minor signs or symptoms of disease
 - 80 = Normal activity with effort
 - 70 = Cares for self. Unable to carry on normal activity or to do active work
 - 60 = Requires occasional assistance but able to care for most of his/her
 - 50 = Requires considerable assistance and frequent medical care
 - 40 = Disabled; requires special care and assistance
 - 30 = Severely disabled; hospitalization indicated though death not imminent
 - 20 = Very sick. Hospitalization necessary. Active support treatment necessary.
 - 10 = Moribund
 - 0 = Dead

APPENDIX B Medications that may cause QTc Prolongation

The following table presents a list of drugs that may prolong the QTc. Patients on these medications are excluded from the study.

Compound				
Alfuzocin	~10 hours		7	
Amantadine	17 +/- 4 hours (10-25)		4	
Amiodarone	58 days (15-142)		180	
(cordarone)	36 days (active metabolite)			
Amitriptyline*	> 24 hours, wide interpatient variability			
Arsenic trioxide	Not characterized			
Azithromycin	40 hours			
Bepridil	42 hr (26-64)		10	
Chloral hydrate	Readily converted to Trichloroethanol (active metabolite $T_{1/2}$ =7-10 hour)	48		
Chloroquine	Prolonged (days to weeks)			
Chlorpromazine	30 +/- 7 hours		7	
Cisapride	6-12 hour, up to 20 hour	60		
Clarithromycin	• Non linear PK3-4 hr (250mg Q12) 5-7 hr (500mg Q12)	36		
Cloroquine	6 to 60 days; mean 20 days			
Desipramine*	> 24 hours, wide interpatient variability			
Disopyramide	6.7 hr (4-10)	36		
Dofetilide	10 hr	48		
Dolesetron	8.1 hr			
Domperidone	7-8 hr	48		
Doxepin*	> 24 hours, wide interpatient variability			
Droperidol	2.2 hours	10		
Erythromycin	* Each salt form has different Half life*			
Felbamate	20-23 hr		5	
Flecainide	20 hr (12-27)		5	
Foscarnet	87.5+/-41.8 hours *distribution and release from bone*		20	
Fosphenytoin	12-29 hr		6	
Gatifloxacin	7-14 hr	48		
Gemifloxacin	7 hours	48		
Grepafloxacin	16 hr		3	
Halofantrine	6-10 days (variable among individual)		45	
Haloperidol	18 +/-5 hr		5	
Ibutilide	6 hours (2-12) * variable among subject*	36		
Imipramine*	> 24 hours, wide interpatient variability			
Indapamide	14 hours (biphasic elimination)		3	
Isradipine	8 hours (multiple metabolites)	48		
Levofloxacin	6-8 hours	48		

Levomethadyl	Multiple compartment PK with active metabolite 2.6 day for LAAM, 2 day for nor-LAAM, 4 day		
	for dinor-LAAM		
Compound	Compound Half Life	Possible Washout Period - Hours	Possible Washout Period - Days
Lithium	24 hour (10-50)		7
Mesoridazine	24-48 hours (animal study)		10
Methadone	15-30 hours		7
Moexipril/HCTZ	2-9 hour (include active metabolite) for moexipril; 5.6-14.8 hours for HCTZ	48	
Moxifloxacin	12 +/-1.3 hours		
Naratriptan	6 hours	36	
Nicardipine	~ 2 hour post IV infusion	12	
Nortriptyline*	> 24 hours, wide interpatient variability		
Octreotide	1.7 hours	12	
Ofloxacin	5 to 7.5 hours		2
Ondansetron	4 hours (IV/IM); 3 hours (PO)		1 to 3
Pentamidine	6.4+/-1.3 hours	36	
Pimozide	55 hours		10
Procainamide	3-4 hour for PA and NAPA (active metabolite)	24	-
Protiptyline*	> 24 hours, wide interpatient variability		
Quetiapine	6 hours	36	
Quinidine	6-8 hours in adult; 3-4 hours in children	36	
Quinine	4-5 hours		
Risperidone	3-20 hours (extensive to poor metabolizer) 9-hydroxyrisperidone (active metabolite) T ½ =21-30 hours (extensive to poor metabolizer)		4
Salmeterol	5.5 hours (only one datum)	36	
Sotalol	12 hours	72	
Sparfloxacin	20 hours (16-30)		4
Sumatriptan	2.5 hours	12	
Tacrolimus	~34 hours in healthy; ~19 hours in Kidney transplant		7
Tamoxifen	5-7 days (biphasic)		30
Telithromycin	2-3 hr	24	
Thioridazine	20-40 hours (Phenothiazines)		7
Tizanidine	2.5 hours	12	
Vardenifil	4 to 5 hours		
Venlaflaxine	5 +/-2 hours for parent comp. 11+-2 hours for OVD (active metabolite)	60	
Voriconizole	6 hours; dose dependent		
Ziprasidone	7 hr	36	
Zolmitriptan	2.8-3.7 hours (higher in female)	18	

APPENDIX C Potential Drug Interactions With Selumetinib

Changes to, or addition of, the following medications should be avoided, unless clinically indicated:

Strong inhibitors of CYP3A4 or fluconazole (strong CYP2C19/ moderate CYP3A4 inhibitor)

Strong inhibitors of CYP3	A4 or fluconazole (strong CYP2C19/ moderate CYP3A4 inhibitor)
	CYP3A4
	Indinavir
	Nelfinavir
	Ritonavir
	Clarithromycin
	Itraconazole
	Ketoconazole
	Nefazodone
	Saquinavir
	Suboxone
	Telithromycin
	Aprepitant
	Erythromycin
	Fluconazole
	Grapefruit juice
	Verapamil
	Diltiazem
	Strong / moderate Inducers of CYP3A4
	CYP3A4
	Efavirenz
	Nevirapine
	Barbiturates
	Carbamazepine
	Glucocorticoids
	Modafinil
	Oxcarbazepine
	Phenobarbital
	Phenytoin
	Pioglitazone
	Rifabutin
	Rifampin
	St John's wort

Strong inhibitors of CYP3A4 or fluconazole	(strong CYP2C19/ moderate CYP3A4 inhibitor))
--	---	---

Strong innocors of C113/5	CYP3A4
	Troglitazone

When AZD 6244 is co-administered with compounds classified as inhibitors, increased plasma concentration of AZD 6244 is the potential outcome. The co-administration of "inducers" would potentially lower plasma AZD 6244 concentrations.

- (1) Gorski, et al. (2004). Clin Pharmacol Ther. 75:89-100.
- (2) Saruwatari, et al. (2003). J Pharm Pharmacol. 55:1553-1559.

APPENDIX D: Dose Reduction Guide for Selumetinib

Body Surface Area (m ²)		Selumetinib dose (mg) Dose level 0			First dose reduction (mg)		
					Dose level -1		
] [a	am	pm		am	pm	
0.55 to 0.69	7	10	10		10	Zero	
0.7 to 0.89		20	20		20	10	
0.9 to 1.09	1 [25	25		25	10	
1.1 to 1.29	1 [30	30		25	20	
1.3 to 1.49	1 [35	35		25	25	
1.5 to 1.69	1 [40	40		30	30	
1.7 to 1.89	7 [45	45		35	30	
1.9 to \geq 2.0		50	50		35	35	

For all patients, dosing will be based on BSA.

Dosing Table for AZD 6244 20 mg/m2 BID

Dose Level	BSA Adjusted Total Daily	BSA	Range	Morning Pills Required		Evening Pills Required	
(mg/m ² BID	Dose (mg)	low	high	10 mg	25 mg	10 mg	25 mg
	20	0.50	0.65	1	0	1	0
	30	0.66	0.81	2	0	1	0
	35	0.82	0.93	0	1	1	0
	40	0.94	1.06	2	0	2	0
	45	1.07	1.18	0	1	2	0
	50	1.19	1.31	0	1	0	1
^	55	1.32	1.43	3	0	0	1
20 mg/m² BID	60	1.44	1.56	3	0	3	0
n^2	65	1.57	1.68	1	1	3	0
1/80	70	1.69	1.81	1	1	1	1
0 п	75	1.82	1.93	4	0	1	1
61	80	1.94	2.06	4	0	-4	0
	85	2.07	2.18	2	1	4	0
	90	2.19	2.31	2	1	2	1
	95	2.32	2.43	0	2	2	1
	100	2.44	2.56	0	2	0	2
	105	2.57	2.68	3	1	0	2
	110	2.69	2.81	3	1	3	1
	115	2.82	2.93	1	2	3	1
	120	2.94	3.00	1	2	1	2

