TITLE: Phase 2 trial of selumetinib in patients with Neurofibromatosis type II related tumors

Coordinating Center: CCHMC

Sponsor Investigator/Study Chair: [name]

Cancer and Blood Diseases Institute

Cincinnati Children's Hospital Medical Center

[name]

[name]

[name] [contact]

[contact]

Email: [contact]

This protocol is for research purposes only, and should not be copied, redistributed or used for any other purpose. The procedures in this protocol are intended only for use by clinical oncologists in carefully structured settings, and may not prove to be more effective than standard treatment. A responsible investigator associated with this clinical trial should be consulted before using or attempting any procedure in this protocol. Contents of this document may not be extracted without permission from the Study Chair.

Other Agent Name(s), NSC# and Supplier: Selumetinib (AZD6244) (AstraZeneca), NSC# 772256

IND Sponsor: [name], Cincinnati Children's Hospital Medical Center/IND# TBD

Protocol Type/ Version#/ Version Date: Original / Version #2.0 / Version Date: 14 December 2016

SCHEMA

Description

This is a single institution, Phase 2 trial for patients with neurofibromatosis type 2 (NF2) with vestibular schwannomas (VS) who exhibit hearing loss. Bilateral vestibular schwannomas (VS) are the hallmark of NF2. As these tumors enlarge, they cause sensorineural hearing loss and, ultimately, complete hearing loss.

Selumetinib (AZD6244) is a highly selective, orally bioavailable, non-ATP competitive small molecule inhibitor of the mitogen-activated protein (MAP) kinase MEK-1/2. MAPK activation in NF2 has been most thoroughly described in schwannomas and elevated MEK1/2 and ERK1/2 have been demonstrated in human schwannoma tissue at both the mRNA and protein levels.

Schema

This is a Phase 2 trial to assess the hearing response rate and radiographic response of VS in children and young adults with NF2 who are treated with selumetinib. Dosing is based on BSA calculated at the beginning of each course.

Selumetinib is taken orally twice a day continuously. One course is equivalent to 28 days. Therapy may continue for up to two years (26 courses) in the absence of disease progression or unacceptable toxicity.

Dose modifications will be based on Body Surface Area (BSA) dose reduction guidelines in Appendix D.

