5.1 Drug Administration

For stratum 1 and stratum 2 patients with NF2 dosing will be based on BSA. Dosing is based on BSA calculated at the beginning of each course. Selumetinib will be supplied as 10 mg and 25 mg capsules or currently available formulation. Patients will receive selumetinib orally twice daily approximately 12 hours apart. Four consecutive weeks will constitute one course and subsequent courses will immediately follow, with no scheduled break in the administration of the drug.

The recommended dose of selumetinib is 25 mg/m² of body surface area (BSA), taken orally twice daily (approximately every 12 hours).

Dosing is individualised based on BSA (mg/m^2) and rounded to the nearest achievable 5 mg or 10 mg dose (up to a maximum single dose of 50 mg). Different strengths of selumetinib capsules can be combined to attain the desired dose (Table 1). selumetinib is not recommended in patients with a BSA <0.55 m².

Table 1 Dosing scheme of selumetinib 25 mg/m² twice daily

Body Surface Area (BSA)	Dose in mg (twice daily)
$0.55 - 0.69 \text{ m}^2$	10
$0.70 - 0.89 \text{ m}^2$	20
0.90 – 1.09 m ²	25
1.10 – 1.29 m ²	30
1.30 – 1.49 m ²	35
1.50 – 1.69 m ²	40
1.70 – 1.89 m ²	45
≥1.90 m ²	50

Dosing is based on the BSA calculated at the beginning of each course of therapy for all patients. Dosing reduction tables are available in APPENDIX D. Patients will be provided with a Medication Diary for selumetinib, instructed in its use, and asked to bring the diary and pill bottles with them to each appointment.

Selumetinib capsules must be taken whole (do not crush or chew) and should be taken on an empty stomach (no food or drink other than water) either 1 hour before or 2 hours after meals. Selumetinib capsules should be taken with water only.

Participants should be advised to drink plenty of water or take rehydration fluids to avoid dehydration if diarrhea occurs. Patients who vomit a dose of selumetinib should NOT be redosed, and appropriate anti-emetic therapy should be implemented prior to the next scheduled dose.

Participants should avoid excessive exposure to sunlight. Patients should use adequate sunscreen protection if exposure to sunlight is to be anticipated.

During the studies, participants should avoid consuming large amounts of grapefruits, Seville oranges, or any other products that may contain these fruits, e.g., grapefruit juice, as these may affect selumetinib metabolism.

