6.2.1 Criteria for continued treatment after toxicity

The study chair or co-chair must be notified of any dosage modification prior to the implementation of the dose modification.

Dose de-escalations to dose level -1 are permitted. See Appendix D.

All patients who require dose de-escalation from dose level -1 must be taken off treatment.

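### Appendix D, the only dose-reduction guide, holds two conflicting reduced-dose tables, and the second gives some patients their full dose or more

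*Combined protocol and SAP*

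**What the plan says.** Section 5.1 sets the full dose: "The recommended dose of selumetinib is 25 mg/m² of body surface area (BSA), taken orally twice daily". Table 1 there turns this into fixed doses by BSA band, "up to a maximum single dose of 50 mg", and adds that "selumetinib is not recommended in patients with a BSA <0.55 m²".

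For reductions, three places point to Appendix D:

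- The Schema: "Dose modifications will be based on Body Surface Area (BSA) dose reduction guidelines in Appendix D".
- Section 5.1: "Dosing reduction tables are available in APPENDIX D".
- Section 6.2.1: "Dose de-escalations to dose level -1 are permitted. See Appendix D". It also requires any patient who needs a further reduction to come off treatment.

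Table 7 in section 6.2 says when to go down a level but gives no milligram amounts.

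Appendix D then prints two schedules under one dose-reduction title. The first sets level 0 beside level -1, the latter column headed "First dose reduction (mg". The second, "Dosing Table for AZD 6244 20 mg/m2 BID", lists capsule counts for BSA 0.50 to 3.00 m² in different bands. No text says what the second table is for, or that it is superseded.

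**The concern.** The reduced dose is defined only by reference to Appendix D, so two schedules there mean two possible doses for the same patient. The second schedule also appears not to reduce the dose in parts of the BSA range, and to break the single-dose maximum and BSA floor of section 5.1.

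Reductions follow dose-modifying toxicity, including grade 3 and 4 events. A patient given the higher schedule gets a smaller cut than the level -1 column intends, or none. Because only one reduction is allowed, the next toxicity that calls for a reduction ends treatment. The patient may therefore be harmed and taken off drug without a real reduction having been tried. In stratum 1 that could happen before the 24-week hearing assessment.

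**Working it through.** **Inputs**

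- Full daily dose (level 0) by BSA band, from Table 1 in section 5.1 and repeated in Appendix D: 20, 40, 50, 60, 70, 80, 90 and 100 mg.
- Level -1 daily dose for the same bands, from the first table of Appendix D (morning plus evening): 10, 30, 35, 45, 50, 60, 65 and 70 mg. The top band is taken as open-ended above 1.90 m², as in section 5.1.
- Second table of Appendix D: 20 rows, 20 to 120 mg/day.
- Limits from section 5.1: single dose at most 50 mg; BSA at least 0.55 m².

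**Step 1: is the second table internally sound?** Daily dose = 10 × (number of 10 mg capsules) + 25 × (number of 25 mg capsules). For the 105 mg row: morning 3 × 10 + 1 × 25 = 55, evening 2 × 25 = 50, total 105. All 20 rows match their stated totals. One entry in the 80 mg row reads as -4 in the extracted text and was taken as 4, which gives 80. The table is a genuine schedule, not a garbled extract.

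**Step 2: compare daily doses (mg) at each 0.01 m² from 0.55 to 3.00 (246 values).** Examples:

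| BSA (m²) | Full dose | Level -1, first table | Second table | Second table ÷ full dose |
|---|---|---|---|---|
| 0.60 | 20 | 10 | 20 | 100% |
| 0.67 | 20 | 10 | 30 | 150% |
| 0.75 | 40 | 30 | 30 | 75% |
| 1.60 | 80 | 60 | 65 | 81% |
| 1.85 | 90 | 65 | 75 | 83% |
| 2.00 | 100 | 70 | 80 | 80% |
| 2.20 | 100 | 70 | 90 | 90% |
| 2.50 | 100 | 70 | 100 | 100% |
| 2.85 | 100 | 70 | 115 | 115% |

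- Same dose: BSA 0.70-0.81, 0.90-0.93, 1.10-1.18, 1.30-1.31 and 1.50-1.56, that is 12 + 4 + 9 + 2 + 7 = 34 of 246. Everywhere else the second table is higher. From 1.57 m² upward the two never agree.
- Second table equal to full dose: 0.55-0.65 (11 values) and 2.44-2.56 (13), total 24.
- Second table above full dose: 0.66-0.69 (4 values) and 2.57-3.00 (44), total 48.
- Between 0.70 and 2.43 it is a reduction, to 70% to 95% of full dose.

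**Step 3: why it fails at the extremes.** In the 0.55-0.69 band the full dose is 10 mg twice daily, which is 10/0.55 = 18.2 down to 10/0.69 = 14.5 mg/m² per dose. That is already below 20 mg/m². At the top, full dose is held at 50 mg, and 50/2.5 = 20 mg/m², so an uncapped 20 mg/m² schedule meets full dose near 2.5 m² and passes it after that.

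**Step 4: the section 5.1 limits.** From 2.57 m² at least one single dose is 55 mg or more, and the largest is 10 + 2 × 25 = 60 mg, against 50 mg. The first row starts at 0.50 m², against 0.55 m².

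**Step 5: the first table alone.** Level -1 is 50%, 75%, 70%, 75%, 71%, 75%, 72% and 70% of full dose across the eight bands, always a true reduction and within both limits.

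**The case against.** The strongest reply is that the operative rule already picks a table. Section 6.2.1 permits only level -1, and only the first table carries that label; its level 0 column matches section 5.1. The second table has no level label and uses a dose level that the treatment plan never authorises, so it looks like a leftover. That makes the first table the better reading, but it does not settle the text. Both tables sit under the same dose-reduction title, section 5.1 speaks of tables in the plural, 20 mg/m² is a plausible step down from 25, and only the second table gives capsule counts. A dose given after toxicity should not depend on inference.

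Other points reduce the size of the problem and stand:

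- Of the 48 values above full dose, 44 lie where the 50 mg maximum, if applied, would bar the printed dose. It does not prevent the increase at 0.66-0.69, or the non-reduction at 0.55-0.65 and 2.44-2.56.
- The grid is unweighted. From 0.70 to 2.06 m² the tables differ by at most 10 mg/day.
- Sections 6.1 and 6.2.1 require the study chair or co-chair to be told before any dose change, which makes an unnoticed error less likely.
- Starting at 0.50 m² matters little, since section 5.1 already advises against treatment below 0.55.
- An effect on the 24-week endpoint needs a misread table and a further toxicity before week 24. Section 13.1.2 keeps every treated patient evaluable. The effect is possible, not shown.

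**Conclusion.** The concern holds. Appendix D gives two reduced-dose schedules that agree on daily dose at 34 of 246 BSA values and conflict at the other 212, with no statement of which applies. The second is no reduction at 24 values and an increase at 48, all at BSA 0.55-0.69 or 2.44 and above.

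This rests on reading the top band of the first table as open-ended and the stray -4 as 4. The counts describe the BSA range, not patients. How many patients fall at the extremes is not known from the documents, though eligibility from age 3 makes the low end possible. This is a dosing-safety defect; the Simon two-stage calculations in section 13.2 are unaffected. It should be corrected because it bears directly on patients with toxicity and costs almost nothing to remove.

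**What to change.** Keep one reduced-dose schedule in Appendix D and label it level -1. Check it row by row against Table 1 of section 5.1, the 50 mg single-dose maximum and the 0.55 m² floor. The sponsor decides which table was intended. The first meets all three checks as printed; the second would need rework at both ends of the BSA range. If capsule counts are wanted for dispensing, add them to the schedule that is kept. Make the reference in section 5.1 singular.

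The cost is a short amendment to Appendix D and a matching pharmacy sheet, with no extra patients or data.

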APPENDIX E Hearing Response Guidelines:

Clinical criteria for definition of hearing response based on a 50-word hearing test. Upper and lower limits for the 95% critical differences for percentage scores are adapted from Thornton. REF

Baseline word recognition score (%)	cognition difference (%) Re		Progressive hearing loss (%)
0	0–4	≥ 6	n/a
2	0-10	≥ 12	n/a
2 4	0-14	≥ 16	n/a
6	2–18	≥ 20	0
8	2–22	≥ 24	0
10	2–24	≥ 26	0
12	4–26	≥ 28	≤ 2
14	4–30	≥ 32	= 2 ≤ 2
16	6–32	≥ 34	-
18	6–34	≥ 36	≤ 4
20	8–36	≥ 38	≤ 6
22	8–40	≥ 42	≤ 6
24	10–42	≥ 44	-
26	12–44	≥ 46	≤ 10
28	14-46	≥ 48	≤ 12
30	14–48	≥ 50	≤ 12
32	16–50	≥ 52	- 12 ≤ 14
34	18–52	≥ 54	≤ 16
36	20–54	≥ 56	≤ 18
38	22–56	≥ 58	≤ 20
40	22-58	≥ 60	≤ 20
42	24–60	≥ 62	≤ 22
44	26–62	≥ 64	− ≤ 24
46	28-64	≥ 66	≤ 26
48	30–66	≥ 68	≤ 28
50	32–68	≥ 70	≤ 30
52	34–70	≥ 72	≤ 32
54	36–72	≥ 74	≤ 34
56	38-74	≥ 76	≤36
58	40–76	≥78	≤38
60	42-78	≥ 80	≤ 40
62	44–78	≥ 80	≤ 42
64	46–80	≥ 82	≤ 44
66	48-82	≥ 84	≤ 46
68	50-84	≥ 86	≤ 48
70	52-86	≥ 88	≤ 50
72	54–86	≥ 88	≤ 52

Baseline word recognition score (%)	95% critical difference (%)	Hearing Response (%)	Progressive hearing loss (%)
74	56–88	≥ 90	≤ 54
76	58–90	≥ 92	≤ 56
78	60–92	≥ 94	≤ 58
80	64–92	≥ 94	≤ 62
82	66–94	≥ 96	≤ 64
84	68–94	≥ 96	≤ 66
86	70–96	≥ 98	≤ 68
88	74–96	≥ 98	≤ 72
90	76–98	100	≤ 74
92	78–98	100	≤ 76
94	82–98	100	≤ 80
96	86–100	n/a	≤ 84
98	90–100	n/a	≤ 88
100	96–100	n/a	≤ 94

APPENDIX F – Participant Diary

STUDY:	DRUG:		Amount (mL/# of pi	lls):			
Patient initials/ID number:	Dose:	1	Dose Frequency:		Cycle Number:		
Week # Date							
	AM PM	AM PM	AM PM	AM PM	AM PM	AM PM	AM PM
Time dose taken*							
Indicate reason for missed doses							
SIDE EFFECTS							
Nausea (see scale below)†							
Vomiting (# of times in 24 hr)							
Diarrhea (# of times in 24 hr)							
Constipation $^{\infty}$							
OTHER SIDE EFFECTS (list below)							
OTHER MEDICATIONS (Name)	Dose	Frequency	Start Date	Stop Date	Reaso	on for Use of Me	dication
+ I(·			·

Parent/patient signature

Date

^{*} If you miss a dose write "M" in the box.

[†] Rate nausea **mild** if you are able to eat and drink a reasonable amount, **moderate** if you can eat and drink but the amount is substantially decreased, or **severe** if you are unable to eat and drink.

[∞] Indicate # of bowel movements/day

SUBJE	CT IDENTIFIER:	
	INSTRUCTIONS FOR COMPLETING THE NI	FTI-QOL
	Please complete the following information	n:
	Age: years	
	Gender: Male 1 Female 2 (please tick	x)
Fo	or each of the questions on the next page, please tick t	the one box tha
	describes how you feel today	
Usual a	activities include: work; housework; study; sport; soc activities	ial; family or l
Guy's NFTI-QOL		
Q1. Do bala	ance or dizziness problems stop you performing your	usual activitie
	No balance problems or dizziness	0 0
	Balance or dizziness problems but no difficulties	□ 1
	Balance or dizziness problems cause me some difficulties	
	Balance or dizziness problems stop my usual activities	1 3
Q2. Do hea	aring problems stop you performing your usual activi	ties?
	No hearing problems	0 o
	Hearing problems but no difficulty	1
	Hearing problems cause me some difficulty	
	Hearing problems stop my usual activities	1 3
Q3. Does fa	acial weakness stop you performing your usual activi	ties?
	No facial weakness	D o
	Facial weakness, but no difficulty	
	•	
	Facial weakness causes some difficulty	□ 2

Sight problems, but no difficulty	□1			
Sight problems cause me some difficulty	\square_2			
Sight problems stop my usual activities	\square_3			
Q5. Do you have any problems in mobility and walki	ng?			
No problems in mobility and walking				
Some difficulty but can manage on my own				
Unable to walk around without some help	\square_2			
Unable to walk at all	□3			
Q6. Has your medical condition affected your role an (e.g., confidence, vulnerability, relationships, caring to				
No effect or positive effect				
Small negative effect				
Moderately negative effect	□ ₂			
Large negative effect	□3			
Q7. Pain; throughout our lives, most of us have had pheadaches, sprains and toothaches. Have you had pain				
None	\square_0			
Mild pain				
Moderate pain	\square_2			
Severe pain	\square_3			
Q8. Do you currently suffer from anxiety or depression?				
No	\square_0			
Mild anxiety or depression				
Moderate anxiety or depression	\square_2			
Extreme anxiety or depression	Пз			

